6.1.6. End of Study/Early Termination

All subjects will return to the site for subsequent EOS assessments 14 (+2) days after receiving their last dose in Treatment Phase 2.

If a subject is terminated early from the study, a PK sample and a blood sample for chemistry and hematology will be drawn as soon as possible together with any relevant safety assessments.

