1.1. STUDY OVERVIEW

This is a prospective, open-label, one-sequence, inpatient, clinical study of CYP2D6 normal metabolizer (NM) subjects with moderate to severe negative symptoms of schizophrenia. be coadministered to subjects already being administered roluperidone to determine its effect on the PD and PK of roluperidone. Eligible subjects will undergo 3 study phases as follows:

- Screening Phase: Between 2 and up to 28 days during which study eligibility will be established and subjects receiving psychotropics will be washed out. Discontinuation of psychotropics must occur at least 2 days prior to the start of Treatment Phase 1 (Day 1). Subjects will be admitted to the site on Day -2 and complete a Baseline Visit on Day -1.
- Treatment Phase 1: After the Baseline Visit (Day -1), roluperidone 64 mg/day will be administered as a monotherapy for 7 days (Days 1-7).
- Treatment Phase 2: Concomitant administration of olanzapine 10 mg/day and roluperidone 64 mg/day for 10 days, starting on Day 8 (Days 8-17). Subjects may be discharged from the clinic at least 48 hours after the last administration of the study drugs and after the collection of the last plasma sample; however, the inpatient period may be extended at the discretion of the investigator.

An End of Study (EOS) visit will take place at least 14 days after the last dose of study treatment. After the EOS visit, the medications and clinical care of the subject will be managed as per the judgement of the investigator/clinician.

Statistical Analysis Plan Final Version

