All adverse events will be recorded on the Adverse Event page of the CRF.

Serious Adverse Event (SAE)

An SAE is defined as any AE that results in any of the following:

- **Death**: The subject died as the result of the event.
- **Life-threatening event**: Any AE that places the subject, in the view of the Investigator or Sponsor, at immediate risk of death from the AE as it occurred, i.e., does not include an AE that had it occurred in a more severe form, might have caused death.
- Required or prolonged inpatient hospitalization: The AE resulted in hospitalization or prolonged an existing hospitalization. Since hospitalization may be part of the study, only hospitalizations that are longer than expected based on Investigator judgment, will be considered prolonged hospitalizations.

Final Version

- **Persistent or significant disability/incapacity**: An AE that results in a substantial disruption of a person's ability to conduct normal life functions.
- Congenital anomaly/birth defect: A congenital anomaly/birth defect that occurs in the offspring of a subject exposed to the Investigational Product.
- Important medical events: An AE that may not result in death, be life-threatening, or require hospitalization may be considered an SAE when, based upon appropriate medical judgment, the event may jeopardize the subject and may require medical or surgical intervention to prevent one of the outcomes listed above.

Treatment-emergent Adverse Event (TEAE)

Any recorded Adverse Event that occurs on or after the initiation of study drug is considered treatment-emergent. TEAEs will be attributed to the most recent treatment group that was received prior to the start of the AE. For AEs with partial dates, the event will be attributed to the earliest period the event could have occurred in based on the date. AEs that occur on a Day 1 of any Treatment Phase with no time will be attributed to the treatment received on that day.

Adverse Event of Special Interest (AESI)

AESIs are defined as the any of the following events:

- Syncope
- Sudden death, cardiac death
- TdP, QT/QTc prolongation, long QT syndrome
- ECG T wave and U wave abnormalities
- Ventricular arrhythmia, tachycardia, fibrillation / flutter

Treatment-emergent Clinically Significant Laboratory Abnormality

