5. STATISTICAL METHODS

Descriptive statistical methods will be used to summarize the data from this study. Unless stated otherwise, the term "descriptive statistics" refers to number of subjects (n), mean, median, standard deviation (SD), minimum and maximum for continuous data and frequencies and percentages for categorical data, and coefficient of variation (%CV) for PK analysis. All data collected during the study will be included in data listings. Unless otherwise noted, the data will be sorted first by treatment, subject number, and then by date within each subject number. For all other tables presenting data collected on-treatment, summaries will be presented by treatment group.

The term 'treatment group' refers to the administration of roluperidone alone or concomitantly with olanzapine to yield 2 groups.

The statistical analyses will be conducted with the SAS® System version 9.4 or higher. All analyses will be subject to formal verification procedures. Specifically, results will be verified utilizing independent programming prior to issuance of the draft statistical report. All documents will be verified by the lead statistician to ensure accuracy and consistency of analyses.

Final Version

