5.3. SAFETY ANALYSES

5.3.1. Adverse Events

Adverse events will be mapped to a Medical Dictionary for Regulatory Activities (MedDRA) version 26.1 preferred term and system organ classification. If a subject experiences multiple events that map to a single preferred term during the same treatment phase, the greatest severity grade and strongest investigator assessment of relation to study medication will be assigned to the preferred term for the appropriate summaries. Should an event have a missing severity or relationship, it will be classified as having the highest severity and/or strongest relationship to study medication.

The occurrence of TEAEs will be summarized by treatment group using preferred terms (PT), system organ classifications (SOC), severity, and/or relationship. A similar summary of (Serious) TEAEs related to study drug will be generated. Separate summaries of treatment-emergent SAE, events of special interest, events leading to the discontinuation of roluperidone, and events leading to death will be generated by SOC and PT. Additionally, an overall summary of the number of subjects experiencing each of these types of TEAEs, along with the overall number of events of each type will be presented. All adverse events reported will be listed for individual subjects showing both verbatim and preferred terms. All adverse events that occurred prior to the initiation of study treatment will be excluded from the tables but will be included in the listings. Any treatment-emergent adverse events occurring after the EOS visit will not be summarized.

The overall summary table will include following types:

- Any TEAE
- Any serious TEAE

Final Version

- Any drug related TEAE
- Any drug related serious TEAE
- Any AESI TEAE
- TEAEs by maximum severity
- TEAEs by maximum relationship
- Any TEAE leading to drug discontinuation
- Any TEAE leading to death

Missing onset dates will be imputed as previously outlined in Section 3.2.3.1 as required to determine treatment-emergent events.

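### For subjects who complete Phase 2, the TEAE tables set 7 days of roluperidone alone against 24–26 days under co-administration, 14–16 of them after the last dose, with no follow-up column or subject-days

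*SAP*

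**What the plan says.** - **Attribution.** SAP 3.2.5 treats any adverse event from first study drug onward as treatment-emergent, and "TEAEs will be attributed to the most recent treatment group that was received prior to the start of the AE". No end point tied to the last dose is given.
- **Columns.** In SAP 5 the term treatment group "refers to the administration of roluperidone alone or concomitantly with olanzapine to yield 2 groups". There is no third, post-treatment group.
- **Tables.** SAP 5.3.1 summarises TEAEs by treatment group and adds an "overall summary of the number of subjects experiencing each of these types of TEAEs, along with the overall number of events of each type". The upper limit is the EOS visit: "Any treatment-emergent adverse events occurring after the EOS visit will not be summarized".
- **Listings.** SAP 5.3.1 also provides that "All adverse events reported will be listed for individual subjects showing both verbatim and preferred terms".
- **EOS timing.** Protocol 6.1.6 places "EOS assessments 14 (+2) days after receiving their last dose in Treatment Phase 2", and the visit schedules in both documents show Day 31 (+2). SAP 1.1 is looser: the "visit will take place at least 14 days after the last dose of study treatment", which sets no upper limit.
- **Early leavers.** Under Protocol 6.1.6, a PK sample and safety bloods "will be drawn as soon as possible together with any relevant safety assessments".

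The table list in SAP 9 contains no exposure table and no rate per unit of time. Days on Study (SAP 3.2.5) is one figure for the whole study, not divided by treatment.

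**The concern.** Two columns of percentages side by side invite comparison, and these two cover different lengths and kinds of time. The roluperidone-alone column stops when olanzapine starts. For a completer, the co-administration column runs through ten dosing days and then about two weeks without study drug, most of it after the earliest permitted discharge. A higher percentage there may reflect only the longer window. A similar percentage may hide a difference during dosing. From the tables alone, a reader can neither separate dosing-period from post-dosing events nor see how much time each column represents.

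This bears on the SAP's primary objective, the safety and tolerability of co-administration. It covers the table of events of special interest, which include syncope and QT prolongation.

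**Working it through.** **1. Reproduce the plan's own dates.** Last dose is on Day 17 (SAP 1.1). EOS = 17 + 14 = Day 31 to 17 + 16 = Day 33, which matches Day 31 (+2) in the schedule. As a cross-check, 28 screening days + 2 pre-dose days + 33 = 63, the maximum study length in the Protocol synopsis.

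**2. Windows for a Phase 2 completer** (last day − first day + 1):

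| Window | Days | Length | Ratio to 7 |
|---|---|---|---|
| Roluperidone alone | 1–7 | 7 | 1 |
| Co-administration, dosing days only | 8–17 | 10 | 1.43 |
| Co-administration, to 48 h after last dose | 8–19 | 12 | 1.71 |
| Co-administration as the SAP counts it | 8–31 to 8–33 | 24–26 | 3.43–3.71 |

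Days after the last dose: 31 − 17 = 14 (14/24 = 58%) to 33 − 17 = 16 (16/26 = 62%). The design explains the step from 7 to 10 days; the counting rule explains the step from 10 to 24–26.

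**3. Illustration of size.** The documents give no adverse event rate. Assume a constant rate *h* = 0.02 per day, equal in both phases and after dosing. Incidence over *d* days is 1 − exp(−*h·d*):

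- 7 days: 1 − exp(−0.14) = 13.1%
- 10 days: 1 − exp(−0.20) = 18.1%
- 12 days: 1 − exp(−0.24) = 21.3%
- 24 days: 1 − exp(−0.48) = 38.1%
- 26 days: 1 − exp(−0.52) = 40.5%

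Over *h* = 0.01 to 0.05, the ratio of 24-day to 7-day incidence runs from 3.2 down to 2.4.

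**4. Sensitivity to post-dosing events.** If events from Day 20 are detected at a fraction *k* of the inpatient rate, the effective window is 12 + 12*k* days (EOS on Day 31). *k* = 0.5 gives 18 days and 30.2%; *k* = 0.25 gives 15 days and 25.9%. If nothing occurred after Day 17, the column would read the 10-day figure, 18.1%.

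With 12 completers, expected subjects with an event are 12 × 0.131 = 1.6 for Days 1–7 and 12 × 0.213 = 2.6 for Days 8–19. To EOS they are 4.6, 3.6 or 3.1 at full, half or quarter detection. Time beyond Day 19 thus adds about 2.0, 1.1 or 0.5 subjects.

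**5. Partial dates.** SAP 3.2.5 places an event with a partial date in the earliest period in which it could have occurred. SAP 3.2.3.1, read as applying to the event, sets a missing start day in the dosing month to the day of first dose. If Day 1 is the 1st of a month, an event on the 25th (Day 25, eight days after the last dose) with the day unknown would be set to Day 1, under roluperidone alone. A follow-up column alone would not correct this.

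**The case against.** The strongest reply is that little turns on these columns. The TEAE summaries carry no test, threshold or decision rule. The design is open-label with one fixed sequence and about 12 completers, so order confounds the two columns however time is counted. Event listings, the drug-administration listing and the Study Day definition allow each onset to be set against the last dose by hand. Laboratory values, vital signs, ECG, AIMS, BARS and C-SSRS are summarised by time point as well as treatment group, so EOS results appear separately. All of this stands. It limits the point to the TEAE tables and to their presentation. It does not make the percentages comparable.

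Several stronger readings are tempting but not supported:

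- **Equal percentages would mean a daily rate 3.4 times lower on co-administration.** The ratio 24/7 belongs to the whole window from Day 8 to EOS. If few events follow dosing, the relevant ratio is near 10/7 = 1.4.
- **Assessment of the primary objective fails.** SAP 2 lists seven kinds of assessment without ranking them, and nothing calls the TEAE tables the main one.
- **58–62% of the column is time free of drug.** That share counts from the day after the last dose. The documents give no half-life, so when exposure ends is unknown. With a Day 19 cut-off, follow-up would be 12/24 = 50% to 14/26 = 54%.
- **The rule inflates co-administration by a known amount.** Every percentage above rests on assumed rates. For early dropouts, the rule can also place post-dosing days under roluperidone alone, though prompt early-termination assessments may keep that time short.

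**Conclusion.** The concern holds for the TEAE tables. For a completer, the SAP's rules compare 7 days with 24–26 days, 14–16 of which follow the last dose, when dosing days alone would be 10 against 7. These figures follow from the documents, given an EOS visit within the 14 (+2) day window; under SAP 1.1's open-ended wording the second window could be longer. The percentages are therefore not comparable between columns and mix two kinds of time.

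The consequence for any reported percentage cannot be fixed from the documents. The 13.1% against 38.1% is an illustration at an assumed equal 2% per day and shrinks if fewer events are detected after discharge. Attribution to the most recent treatment is not wrong in itself; what is missing is a post-treatment split and a denominator of time. Because the analysis is descriptive and the listings are complete, this ranges from a minor point to one that should be fixed because the fix is cheap. It does not invalidate the safety analysis.

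**What to change.** In SAP 3.2.5, 5 and 5.3.1:

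- Keep the co-administration total, so that no signal is hidden, and split it into on-treatment and post-treatment follow-up. On-treatment would run from the Day 8 dose to a pre-specified cut-off after the last dose, for example the 48-hour assessment on Day 19. State the reason for the cut-off and use one definition throughout. SAP 5.3.2 already separates laboratory shifts to 48 hours post-dose from shifts to EOS.
- Show subject-days at risk for each column.
- Apply the same last-dose rule to early dropouts in both treatment groups.
- State how events with partial start dates are placed among the three windows (roluperidone alone, on-treatment co-administration, follow-up), and flag them.

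Optional and separate: SAP 5.3.1 keeps all post-EOS events out of the summaries, while Protocol 9.2.1 requires reporting of serious events notified spontaneously within 30 days of the last dose. For a completer that is Day 17 + 30 = Day 47, 14–16 days after EOS. Such serious events and deaths could be tabulated if they are in the database at lock, marked as passively reported. The documents do not say how these reports reach the database, so any that arrive after lock would still be left out.

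The cost is SAP wording and modest programming. Dose times, event dates and the final study day are already collected. Tables become wider and sparser with 12–18 subjects, and confounding by treatment order remains.

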3.2.3.1. Missing Dates

An incomplete date is any date for which either the day, month or year is unknown, but all three fields are not unknown. An incomplete date occurs when the exact date an event occurred or ended cannot be obtained from a subject.

For many of the analyses, a complete date is necessary in order to determine if the event should be included in the analysis (i.e., if the event is treatment-emergent) or to establish the duration of an event. In such cases, incomplete dates will be imputed.

For the purposes of handling partially reported start and stop dates for an event the following algorithm will be applied:

• Missing start day, but month and year present:

If the event occurs in the same month and year as the dosing of the study drug, then the start day of the study drug will be assigned to the day of first dose of the study drug.

Otherwise, the start day will be set to the first day of the month.

• Missing start day and month, but year present:

If event occurs in the same year as the study drug dosing, then the start date of the event will be assigned to Day 1 of Treatment Phase 1.

Otherwise, the start day and month will be set to 01 January.

• Missing all components of a start date:

Assign the date of Day 1 of Treatment Phase 1.

• Missing end day, but month and year present:

The day will be set to the last day of the month.

• Missing end day and month, but year present:

The end day and month will be set to the date of study completion (EOS Visit Date).

However, if the study completion year is greater than the year of the event, then the day and month will be set to 31 December.

• In the event of a completely missing end date (year not present and ongoing not checked), the end date will be imputed as the date of study completion or discontinuation. If the imputed date is later than the date of study withdrawal, then the date of study withdrawal will be imputed for the date.

If any imputed date causes the end date to occur prior to the start date of the event, the start date of the event will be used for the imputation of the end date. If any imputed date causes the start date of the event to occur after the end date of the event, the end date of the event will be used for the imputation of the start date. In subject data listings, start and stop date of events will be displayed as reported on the eCRF (i.e., imputed values will not be listed).

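### The SAP's incomplete-date rules can move adverse events from the combination phase to roluperidone alone, but never the other way

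*SAP*

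**What the plan says.** Treatment-emergent adverse events (TEAEs) are tabulated by treatment group, roluperidone alone or roluperidone with olanzapine (SAP 5 and 5.3.1). SAP 3.2.5 gives three attribution rules:

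- In general, "TEAEs will be attributed to the most recent treatment group that was received prior to the start of the AE".
- With a partial date, "the event will be attributed to the earliest period the event could have occurred in based on the date".
- With only the time missing, "AEs that occur on a Day 1 of any Treatment Phase with no time will be attributed to the treatment received on that day". An event on Day 8 then counts as combination.

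SAP 5.3.1 refers to SAP 3.2.3.1 for imputing missing onset dates:

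- Day missing: "If the event occurs in the same month and year as the dosing of the study drug", the day of first dose is used. "Otherwise, the start day will be set to the first day of the month".
- Day and month missing: if the year is the dosing year, "then the start date of the event will be assigned to Day 1 of Treatment Phase 1". For any other year the rule reads: "Otherwise, the start day and month will be set to 01 January".
- Everything missing: "Assign the date of Day 1 of Treatment Phase 1".

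If an imputed start falls after the end date, the end date is used instead, which can only move onset earlier. No analysis under the opposite attribution is planned.

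**The concern.** The order of treatment is the same for everyone: roluperidone alone on Days 1-7 and the combination on Days 8-17 (SAP 1.1). Where the recorded date allows either phase, the earliest period is therefore the single-drug phase. A rule that would be neutral on average in a randomised crossover favours one column here.

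That column is the reference. The primary objective in SAP 2 is the safety and tolerability of co-administration, so the error makes the combination look safer and the reference look worse. The SAP takes the cautious line for other missing adverse-event fields: in SAP 5.3.1 a missing severity counts as the highest and a missing relationship as the strongest. A missing onset date decides which treatment column the event enters, yet it is resolved in the less cautious direction. For a rare event of special interest, one reassignment could change a combination count from 1 to 0.

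**Working it through.** The documents give no figure for this point, so there is none to reproduce. The check has three parts.

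**1. Direction.** For a true onset on or after Day 1, the imputed start is either Day 1, the 1st of the recorded month, or 1 January of the recorded year. None of these is later than the true onset when it is used, and the end-date rule only moves a start earlier. So imputed start ≤ true onset in every case. A Day 8+ onset can move to Days 1-7, but a Day 1-7 onset cannot move to Day 8 or later.

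**2. How often an incomplete date moves.** Inputs:

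- Phases: Days 1-7 alone, Day 8 onward combination (SAP 1.1 and the general rule in 3.2.5).
- End-of-study visit at Day 31 (SAP 1.2). TEAEs after it are not summarised (SAP 5.3.1).
- Inpatient stay to Day 19 (SAP 3.2.4), so Days 20-31 are outpatient.
- Study period October 2023 to February 2024 (Protocol synopsis).

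Assumptions that are not in the documents: Day 1 uniform over 1 October 2023 to 31 January 2024 (123 dates), onset uniform over the stated days, and no end-date override. Each start date is paired with each onset day, for example 123 × 10 = 1,230 pairs for Days 8-17. Share moved = pairs with an imputed start on Days 1-7 / all pairs.

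| True onset | Day missing | Day and month missing | All missing |
|---|---|---|---|
| Days 8-17 | 1,010/1,230 = 82.1% | 1,175/1,230 = 95.5% | 100% |
| Days 8-31 | 1,751/2,952 = 59.3% | 2,652/2,952 = 89.8% | 100% |
| Days 20-31 | 587/1,476 = 39.8% | 1,254/1,476 = 85.0% | 100% |

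All shares are conditional on the date being incomplete.

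Three cases with the day missing:

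- Day 1 = 16 October, onset 25 October (Day 10), recorded as October 2023. Imputed to 16 October = Day 1: moved to roluperidone alone.
- Day 1 = 27 October, onset 5 November (Day 10), recorded as November 2023. Imputed to 1 November = Day 6: moved.
- Day 1 = 20 October, onset 3 November (Day 15), recorded as November 2023. Imputed to 1 November = Day 13: correctly stays in the combination.

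**3. Effect of one moved event on a table row.** Planned numbers are 18 dosed with roluperidone and at least 12 completing the combination (SAP 3.1). The alone column rises by 1/18 = 5.6 points. The combination column falls by between 1/18 = 5.6 and 1/12 = 8.3 points. The contrast changes by 5.6 + 5.6 = 11.1 to 5.6 + 8.3 = 13.9 points.

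This is an upper bound for one event. If the subject already has an event in that row in Phase 1, the alone column does not rise. If the subject has another in Phase 2, the combination column does not fall.

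**The case against.** The case for leaving the rule alone has five parts.

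- **Not every date moves.** A reader might infer that incomplete dates always go back to roluperidone alone. They do not: SAP 3.2.3.1 uses the 1st of the recorded month or year when that is not the dosing month or year, and the result can be Day 8 or later. Only fully missing dates always move. This stands.
- **The rule moves most where gaps are least likely.** The 82% applies to Days 8-17, when subjects are inpatients with daily scheduled assessments. A reader might take the outpatient weeks as the main source of bias, but those days seldom share a calendar month with Day 1: 300/1,476 = 20% of pairs for Days 20-31. With the other rule added, about 40% move and 60% stay. This stands as a limit on size. It does not remove the problem, because Days 20-31 are 12 of the 24 days from Day 8 to Day 31.
- **The effect may be nil.** Subjects are counted once per preferred term and phase, so a moved event may leave a row unchanged. The documents give no expected number of incomplete dates. Both stand.
- **Safety is descriptive, and listings show dates as reported.** With about 18 subjects a reader could reassign an event by hand, and data are cleaned before lock. That helps, but it does not correct the by-treatment tables that address the primary objective.
- **The opposite default has the opposite error.** True. It would sometimes put a Phase 1 event in the combination column. That is the cautious direction for this objective, and showing both attributions makes the difference visible.

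**Conclusion.** The point holds for direction and only conditionally for size. SAP 3.2.5 and 3.2.3.1 together assign all fully missing onset dates, and many partial ones that could belong to either phase, to roluperidone alone, and they never move an ambiguous event into the combination. This follows from the rules themselves and needs no assumption. It works against the primary objective and is out of line with the SAP's worst-case handling of missing severity and relationship.

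The shares moved rest on the uniform-date assumptions above and say nothing about how many dates will be incomplete. That number is unknown and, given the inpatient stay, probably small. The documents do not support reading 11 to 14 points as the expected bias, or as the effect of every moved event. The change is worth making because the rule is one-sided, has no planned check, and is cheap to correct.

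**What to change.** - **SAP 3.2.5:** for subjects who entered Treatment Phase 2, when the recorded information (partial date, end date, other records) does not place onset before Day 8, attribute the event to the combination in the main TEAE tables.
- **Sensitivity:** for any events affected, show the tables or a short listing under the present earliest-period rule. If there are none, say so.
- **SAP 3.2.3.1:** align it with 3.2.5. As written, the earliest period for a date in the dosing month could be read as pre-treatment, while 3.2.3.1 uses the first dose. The missing-day rule also speaks of assigning the start day of the study drug, where the start day of the event appears to be meant.

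The cost is SAP wording and, if events are affected, one extra output. No data collection or trial conduct changes. The downside is that the combination rate may be slightly overstated.
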